6.15. Subgroup Analyses

6.15.1. Efficacy Subgroup Analyses

Subgroup analysis will be conducted for the co-primary endpoints of proportion of patients achieving PASI 75 and sPGA (0,1) response using the ITT Population for Period 2.

Subgroups to be evaluated may include gender, age, weight, ethnicity, region, geographic region, baseline disease severity, duration of disease, previous nonbiologic systemic therapy, and previous biologic therapy.

A logistic regression model with treatment, subgroup, and interaction of subgroup-by-treatment included as factors will be used. The subgroup-by-treatment interaction will be tested at the significance level of 0.10. Treatment group differences will be evaluated within each category of the subgroup using the Fisher's exact test, regardless of whether the interaction is statistically

significant. Missing data will be imputed using NRI. If any group within the subgroup is <10% of the Total ITT Population, only summaries of the efficacy data will be provided (that is, no inferential testing).

The following subgroups will be analyzed:

- Patient Demographics Subgroups:
 - Gender
 - Age Group (years): <12; and ≥12
 - Weight Category: <25 kg; ≥25 to ≤50 kg; and >50 kg (only summary statistics)
 - Ethnicity
- Geographic Region Subgroups:
 - Geographic Region: North America; Europe Union; and Rest of the World
- Baseline Severity of Disease Subgroups:
 - Baseline PASI category: <20; and ≥20
 - Baseline sPGA category: 3; 4; and 5
 - Baseline sPGA category: 3; and combined 4 or 5
 - Baseline BSA category: <20%; and ≥20%
- Previous Psoriasis Therapy Subgroups:
 - Previous Nonbiologic Systemic Therapy (methotrexate, cyclosporine, retinoids, corticosteroid, fumaric acid derivatives, apremilast, psoralen and ultraviolet A [PUVA]): never used; and ever used
 - Previous Biologic Systemic Therapy: never used; and ever used
- Other Patient Characteristics Subgroups:
 - Duration of Disease (in years): >0.5 and ≤1; >1 and ≤1.5; >1.5 and ≤2; and >2

Additional subgroup analyses on efficacy may be performed, as deemed appropriate and necessary.

6.15.2. Safety Subgroup Analyses

Safety subgroup analysis for common TEAEs and AESI of infections and injection site reactions will be summarized for P2 Main Study Safety Population. The common TEAEs will be presented by decreasing frequency of PT within SOC. The infections and injection site reactions will be presented by decreasing frequency of PT

A logistic regression model with treatment, subgroup, and the interaction of subgroup-by-treatment included as factors will be used. The subgroup-by-treatment interaction will be tested at the significance level of 0.10. The response variable will be each AE. Treatment group differences will be evaluated within each category of the subgroup using Fisher's exact test, regardless of whether the interaction is statistically significant. If any group within the subgroup is <10% of the total population, only the descriptive statistics will be provided for that subgroup (that is, no inferential testing).

The following subgroups will be analyzed:

- Weight Category: <25 kg; ≥ 25 to ≤ 50 kg; and >50 kg
- Geographic Region: North America; Europe Union; and Rest of the World

Additional subgroup analyses on safety may be performed, as deemed appropriate and necessary.

6.16. Protocol Deviations

Protocol deviations will be identified throughout the study. Important protocol deviations are defined as those deviations from the protocol likely to have a significant impact on the completeness, accuracy, and/or reliability of the study data, or that may significantly affect subject's rights, safety, or well-being.

The major protocol deviations, which are the subset of the important protocol deviations, are the protocol deviations that might have impact on the efficacy and/or safety results. The impact of major protocol deviations on the efficacy results will be investigated by assessing the robustness of the study results and conclusions to the choice of analysis population, both by including and excluding the data potentially affected by major protocol deviations. As specified in Section 6.1.1, the PPS Population is defined as all randomized patients who do not have major protocol deviations.

Table RHCD.6.12 includes the categories and subcategories of important protocol deviations, whether or not these deviations are major protocol violations, the action to be taken regarding the exclusion of patients from PPS, the source of the deviation identified, and the statistical programming guidance for the clinical study report (CSR).

The number and percentage of patients having important protocol deviation(s) will be summarized within category and subcategory of deviations by treatment group for the ITT Population for the Double-Blind Treatment Period (Period 2).

A by-patient listing of important protocol deviations will be provided.

Table RHCD.6.12. Identification and Action of Important Protocol Deviations

Important Protocol Deviation Category/Subcategory/Study Specific	Action for PPS Analysis	Source to Identify Protocol Deviation ^a	Statistical Programming Guidance for Clinical Study Report
Category: Eligibility			
Subcategory: Inclusion/Exclusion			
[1] No confirmed diagnosis of moderate-to-severe plaque-type Ps for at least 6 months prior to Visit 2	Excluded from PPS	Monitor and Stats	Either from monitor’s list, or, if date of diagnosis of Ps is missing or less than 6 months prior to Visit 2.
[2] PASI score <12 or sPGA <3 or BSA involvement <10% at Visit 1 or Visit 2	Excluded from PPS	Monitor and Stats	Either from monitor’s list, or, If PASI score <12 or sPGA <3 or BSA involvement <10% or any missing at Visit 1 or Visit 2.
[3] Not a candidate for phototherapy or systemic therapy	Excluded from PPS	Monitor	From monitor’s list.
[4] Age <6 years or ≥18 years	Excluded from PPS	Monitor	From monitor’s list.
[5] Improper informed consent	Do not exclude from PPS	Monitor and Stats	Either from monitor’s list, or, if patient informed consent date is after Visit 1 date.
[6] Immunizations are not up to date in agreement with current immunization guidelines	Excluded from PPS	Monitor	From monitor’s list.
[7] Have pustular, erythrodermic, and/or guttate forms of Ps	Excluded from PPS	Monitor	From monitor’s list.
[8] With drug-induced Ps	Excluded from PPS	Monitor	From monitor’s list.
[9] Have clinical and/or laboratory evidence of untreated latent or active TB	Excluded from PPS	Monitor and Stats	From monitor’s list, or If a PPD skin test response of ≥5 mm in duration, or a “positive” for the QuantiFERON-TB® Gold test or T-SPOT.TB test.

Important Protocol Deviation Category/Subcategory/Study Specific	Action for PPS Analysis	Source to Identify Protocol Deviation ^a	Statistical Programming Guidance for Clinical Study Report
[10] Have evidence of or test positive for hepatitis B virus (HBV)	Do not exclude from PPS	Monitor and Stats	
Either from monitor’s list, or, if test positive for HBV at Visit 1 by testing: 1) positive for hepatitis B surface antigen (HBsAg+); or 2) positive for anti-hepatitis B core antibody (HBcAb+) and are HBV deoxyribonucleic acid (DNA) positive.
 
Note: Subjects who are HBcAb+ and HBV DNA negative may be enrolled in the study. Subjects who meet these criteria at screening will be identified by the central laboratory and monitored during the study.

[11] Have evidence of or test positive for hepatitis C virus (HCV)	Do not exclude from PPS	Monitor and Stats	
Either from monitor’s list, or, if test positive for HCV at Visit 1 by testing: 1) positive for hepatitis C antibody (anti-HCVAb); and 2) positive via a confirmatory test for HCV.

[13] Have any varicella-zoster virus infection within 12 weeks of Visit 2	Do not exclude from PPS	Monitor	From monitor’s list.
[22] Presence of significant uncontrolled neuropsychiatric disorder, or have had a recent past history of a suicide attempt, or marked a yes to C-SSRS question 4 or 5 on ideation or yes to suicide behaviors	Do not exclude from PPS	Monitor	From monitor’s list
[24] Have not had any immunizations, or are not up to date on immunizations recommended by country specific Pediatric guidance	Do not exclude from PPS	Monitor	From monitor’s list.
[29] At Visit 1, have a neutrophil count <1500 cells/ μ L (<1.50 \times 10 ⁹ / μ L or <1.50 GI/L), a lymphocyte count <800 cells/ μ L (<0.80 \times 10 ⁹ / μ L or <0.80 GI/L), a platelet count <100,000 cells/ μ L (<100 \times 10 ⁹ / μ L or <100 GI/L)	Do not exclude from PPS	Monitor and Stats	
Either from monitor’s list, or, If have a neutrophil count <1500 cells/μL (<1.50\times10⁹/μL or <1.50 GI/L), a lymphocyte count <800 cells/μL (<0.80\times10⁹/μL or <0.80 GI/L), a platelet count <100,000 cells/μL (<100\times10⁹/μL or <100 GI/L) or missing at Visit 1.

[32] Previously treated with etanercept	Excluded from PPS	Monitor and Stats	
Either from monitor’s list, or, If have etanercept in the CRFs “Prior Therapy: Psoriasis”.

Important Protocol Deviation Category/Subcategory/Study Specific	Action for PPS Analysis	Source to Identify Protocol Deviation ^a	Statistical Programming Guidance for Clinical Study Report
[33] Have used any therapeutic agent targeted at reducing interleukin-17 (IL-17)	Excluded from PPS	Monitor	From monitor’s list.
[35] Had a live vaccination within 12 weeks prior to Visit 2, or intend to have a live vaccination during the course of the study or within 12 weeks of completing treatment in this study, or have participated in a vaccine clinical study within 12 weeks prior to Visit 2	Do not exclude from PPS	Monitor	From monitor’s list.
Category: Study Procedures			
Subcategory: Violation of Discontinuation Criteria			
[D1] ALT or AST >8× ULN	Do not exclude from PPS	Monitor and Stats	Either from monitor’s list, or, if a patient still receives study treatment after 10 days with confirmed ALT or AST >8× ULN (defined as a test of 8× ULN and a retest within 10 days still >8 × ULN; if not retest, use the test as the confirmed).
[D2] ALT or AST >5× ULN for more than 2 weeks	Do not exclude from PPS	Monitor and Stats	Either from monitor’s list, or, if a patient still receives study treatment after 24 days with confirmed ALT or AST >5× ULN (defined as a test of 5× ULN and a retest within 14 days still >5× ULN; if not retest, use the test as the confirmed).
[D3] ALT or AST >3× ULN and TBL >2 × ULN or prothrombin time >1.5 time ULN	Do not exclude from PPS	Monitor and Stats	Either from monitor’s list, or, if a patient still receives study treatment after 10 days with confirmed ALT or AST >3× ULN and TBL >2× ULN or prothrombin time >1.5× ULN (defined as a test of 3× ULN and 2× ULN or 1.5× ULN and a retest within 10 days still >3× ULN and 2× ULN or 1.5× ULN; if not retest, use the test as the confirmed).
[D4] ALT or AST >3× ULN with the appearance of fatigue, nausea, vomiting, right upper-quadrant pain or tenderness, fever, rash, and/or eosinophilia (>5%)	Do not exclude from PPS	Monitor and Stats	Either from monitor’s list, or, If a patient still receives study treatment after 10 days with confirmed ALT or AST >3× ULN with the appearance of fatigue, nausea, vomiting, right upper-quadrant pain or tenderness, fever, rash, and/or eosinophilia (>5%) (defined as a test of 3× ULN and a retest within 10 days still >3× ULN; if not retest, use the test as the confirmed).

Important Protocol Deviation Category/Subcategory/Study Specific	Action for PPS Analysis	Source to Identify Protocol Deviation ^a	Statistical Programming Guidance for Clinical Study Report
[D5] ALP >3× ULN	Do not exclude from PPS	Monitor and Stats	Either from monitor’s list, or, If a patient still receives study treatment after 10 days with confirmed ALP >3× ULN (defined as a test of 3× ULN and a retest within 10 days still >3× ULN; if not retest, use the test as the confirmed).
[D6] ALP >2.5× ULN and TBL >2× ULN	Do not exclude from PPS	Monitor and Stats	Either from monitor’s list, or, If a patient still receives study treatment after 10 days with confirmed ALP >2.5× ULN and TBL >2× ULN (defined as a test of 3× ULN and 2× ULN and a retest within 10 days still >3× ULN and 2× ULN; if not retest, use the test as the confirmed).
[D7] ALP >2.5× ULN with the appearance of fatigue, nausea, vomiting, right upper-quadrant pain or tenderness, fever, rash, and/or eosinophilia (>5%)	Do not exclude from PPS	Monitor and Stats	Either from monitor’s list, or, If a patient still receives study treatment after 10 days with confirmed ALP >2.5× ULN with the appearance of fatigue, nausea, vomiting, right upper-quadrant pain or tenderness, fever, rash, and/or eosinophilia (>5%) (defined as a test of 2.5× ULN and a retest within 10 days still >2.5× ULN; if not retest, use the test as the confirmed).
[D8] Neutrophil counts <500 cells/μL, or ≥500 and <1000 cells/μL based on 2 test results, or ≥1000 and <1500 cells/μL based on 3 test results and a concurrent infection	Do not exclude from PPS	Monitor and Stats	Either from monitor’s list, or, If a patient still receives study treatment after 10 days with confirmed segmented neutrophil counts <500 cells/μL (defined as a test of <500 cells/μL and a retest within 10 days still <500 cells/μL; if no retest, use the test as the confirmed).
[D9] Total WBC count <2000 cells/μL	Do not exclude from PPS	Monitor and Stats	Either from monitor’s list, or, If a patient still receives study treatment after 10 days with confirmed total WBC count <2000 cells/ μL (defined as a test of <2000 cells/μL and a retest within 10 days still <2000 cells/μL; if no retest, use the test as the confirmed)
[D10] Lymphocyte count <200 cells/μL	Do not exclude from PPS	Monitor and Stats	Either from monitor’s list, or, If a patient still receives study treatment after 10 days with confirmed lymphocyte count <200 cells/μL (defined as a test of <200 cells/μL and a retest within 10 days still <200 cells/μL; if no retest, use the test as the confirmed).

Important Protocol Deviation Category/Subcategory/Study Specific	Action for PPS Analysis	Source to Identify Protocol Deviation^a	Statistical Programming Guidance for Clinical Study Report
[D11] Platelet count <50,000 cells/ μ L	Do not exclude from PPS	Monitor and Stats	Either from monitor’s list, or, If a patient still receives study treatment after 10 days with confirmed platelet count <50,000 cells/ μ L (defined as a test of <50,000 cells/ μ L and a retest within 10 days still <50,000 cells/ μ L; if no retest, use the test as the confirmed).
[D12] Subject BP readings are greater than 95 th percentile at 3 consecutive study visits	Do not exclude from PPS	Monitor	From monitor’s list.
[D13] A severe AE or an SAE, or a clinically significant change in a laboratory value	Do not exclude from PPS	Monitor and Stats	Either from monitor’s list, or, If patient still receives study treatment on the same day or after the date with an AE or SAE.
[D14] Clinically significant systemic hypersensitivity reaction that does not respond to treatment	Do not exclude from PPS	Monitor	From monitor’s list.
[D15] Patient became pregnant	Do not exclude from PPS	Monitor	From monitor’s list.
[D16] Patient developed a malignancy (more than 2 nonmelanoma skin cancers)	Do not exclude from PPS	Monitor	From monitor’s list.
[D17] Patient has a positive TB test using PPD or QuantiFERON®-TB Gold	Do not exclude from PPS	Monitor	From monitor’s list.
[D18] Change in disease phenotype	Excluded from PPS	Monitor	From monitor’s list.
[D19] Patient requires treatment with another therapeutic agent that has been demonstrated to be effective for the treatment of Ps	Excluded from PPS	Monitor	From monitor’s list.
[D20] Enrollment in any other clinical trial involving an investigational product or enrollment in any other type of medical research judged not to be scientifically or medically compatible with this study	Excluded from PPS	Monitor	From monitor’s list.
[D21] The investigator or attending physician decides that the patient should be withdrawn from the study treatment	Do not exclude from PPS	Monitor	From monitor’s list.

Important Protocol Deviation Category/Subcategory/Study Specific	Action for PPS Analysis	Source to Identify Protocol Deviation^a	Statistical Programming Guidance for Clinical Study Report
[D22] The patient (or guardian) requests to be withdrawn from the study treatment	Do not exclude from PPS	Monitor	From monitor’s list.
[D23] The patient, at any time during the study, scores ≥ 5 for Item 13 on the CDRS-R. Or	Do not exclude from PPS	Monitor and Stats	Either from monitor’s list, or, score ≥ 5 to Item 13 (Suicidal Ideation) of CDRS-R.
[D24] Develops active suicidal ideation with some intent to act with or without a specific plan	Do not exclude from PPS	Monitor and Stats	Either from monitor’s list, or, yes to question 4 or 5 on the “Suicidal Ideation” Portion of C-SSRS.
[D25] Develops suicide-related behaviors as recorded on C-SSRS	Do not exclude from PPS	Monitor and Stats	Either from monitor’s list, or, yes to question “suicidal behavior” on the “Suicidal Behavior” Portion of C-SSRS.
[D26] It is recommended that the subject be assessed by an appropriately trained professional to assist in deciding whether the subject is to be discontinued from the study	Do not exclude from PPS	Monitor	From monitor’s list.
[D27] Investigator or Lilly stopped the patient participation	Do not exclude from PPS	Monitor	From monitor’s list.
Category: Study Procedures			
Subcategory: Excluded Con-meds	Excluded from PPS	Monitor and Stats	Either from monitor’s list, or If patient takes prohibited concomitant medication. Note: Prohibited concomitant medication will be provided by medical in a separate file.
Subcategory: Other			
Missing CDRS-R total score: missing baseline or any scheduled visit prior to discontinuation visit	Do not exclude from PPS	Stats	If missing CDRS-R total score baseline or any scheduled visit prior to discontinuation visit.
Missing C-SSRS: missing baseline or any scheduled visit prior to discontinuation visit	Do not exclude from PPS	Stats	If missing C-SSRS baseline or any scheduled visit prior to discontinuation visit. C-SSRS is missing if the whole questionnaire is missing.

Important Protocol Deviation Category/Subcategory/Study Specific	Action for PPS Analysis	Source to Identify Protocol Deviation^a	Statistical Programming Guidance for Clinical Study Report
Missing sPGA: not having Week 12 measurement for patients who have completed Week 12	Do not exclude from PPS. Note: such patients will be treated as nonresponders at Week 12	Stats	If not having Week 12 sPGA measurement for patient who have completed week 12.
Missing PASI: not having Week 12 measurement for patients who have completed Week 12	Do not exclude from PPS. Note: such patients will be treated as nonresponders at Week 12	Stats	If not having Week 12 PASI measurement for patient who have completed week 12.
Had unqualified site personnel perform clinical safety and/or efficacy assessments	Do not exclude from PPS	Monitor	From monitor's list.
Missing parents/other adult to respond CDRS-R scale at any visit	Do not exclude from PPS	Monitor	From monitor's list.
Missing or Unqualified blinded assessor	Do not exclude from PPS	Monitor	From monitor's list.
Category: Investigational Product			
Subcategory: Treatment Assignment/Randomization Error			
Took incorrect study medication	Do not exclude from PPS. Analyze "As randomized" or "As assigned."	Stats	If IWRS study drug dispense data not match with the treatment label identifier on the Exposure as Collected eCRF page.
Moderate-to-severe patients from etanercept approved countries randomized as severe	Do not exclude from PPS	Monitor and Stats	Either from monitor's list, or If patient with PASI <20 and sPGA <4 at baseline received etanercept in P2.

Important Protocol Deviation Category/Subcategory/Study Specific	Action for PPS Analysis	Source to Identify Protocol Deviation^a	Statistical Programming Guidance for Clinical Study Report
Subcategory: Compliance	Excluded from PPS	Stats	If non-compliant with study medication regimen or over-dose during the treatment period. Note: Non-compliance with therapy is defined to be missing more than 20% of expected doses and missing 2 or more consecutive doses; over-dose is defined as to take more injections at the same time point than specified in the protocol.
Subcategory: Patient took medication not fit for use	Do not excluded from PPS	Monitor	From monitor's list.
Subcategory: Other			
Randomized but did not take any study medication	Excluded from PPS	Stats	If a patient is randomized but does not take any study medication.
Overdose/ Underdose in terms of actual volume of IP	Excluded from PPS	Monitor	From monitor's list.
Category: Safety			
Subcategory: SAEs			
Failure to report within 24 hours of the PI aware	Do not Excluded from PPS	Monitor	From monitor's list.
Category: Informed Consent			
Subcategory: Informed Consent not Obtained/Missing/Late	Excluded from PPS	Monitor and Stats	Either from monitor's list, or, if patient informed consent date is after Visit 1 date or missing informed consent.
Subcategory: Improper Informed Consent	Do not Excluded from PPS	Monitor	From monitor's list.
Category: Administrative/Oversight			
Subcategory: Reg/Ethic Approvals	Excluded from PPS	Monitor	From monitor's list.
Subcategory: Other			
Enrolled in a site with significant GCP noncompliance issue	Excluded from PPS	Monitor	From monitor's list.

Abbreviations: AE = adverse event; BCG = Bacille de Calmette et Guérin; BSA = body surface area; CDRS-R = Children's Depression Rating Scale–Revised; Con-Meds = concomitant medications; C-SSRS = Columbia–Suicide Severity Rating Scale; DV = protocol deviations; eCRF = electronic case report form; GCP = good clinical practice; IgG = immunoglobulin G; IL = interleukin; ITT = intent-to-treat; IV = intravenous; IWRS = interactive web-response system; PASI = Psoriasis Area and Severity Index; PPD = purified protein derivative; PPS = per protocol set; Ps = psoriasis; PsA = psoriatic arthritis; Reg = regulatory; SAE = serious adverse event; sPGA = static Physician Global Assessment; stats = statistics; TB = tuberculosis; TBL = total bilirubin.

^a The term “Monitor” indicates the protocol deviation will be identified by site monitors and entered into monitor’s list using a spreadsheet. The spreadsheet will be exported as Study Data Tabulation Model (SDTM) DV domain.

The term “Stats” indicates the protocol deviation will be programmed based on data in clinical database by statistical programmers with the statistical programming guidance provided as the last column. The detailed programming specification will be documented in Analysis Data Model (ADaM) specification.

The terms “Monitor and Stats” indicates the protocol deviation will be a combination of monitor’s list (SDTM.DV domain) and statistical programming from clinical database, the deviation will show if either source identifies.

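### The programmed flag for TB eligibility deviation [9] ignores treatment status, so a subject with treated latent TB would be dropped from the per-protocol set against the row's own definition

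*SAP*

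**What the plan says.** All of this is in SAP Section 6.16, Table RHCD.6.12 and its footnote.

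- **Row [9], definition.** Under the eligibility category, inclusion/exclusion subcategory: "Have clinical and/or laboratory evidence of untreated latent or active TB". The action is exclusion from the PPS, and the source is the monitor together with statistical programming.
- **Row [9], programming guidance.** Besides the monitor's list, the trigger is "If a PPD skin test response of ≥5 mm in duration", or a positive result on the QuantiFERON-TB "Gold test or T-SPOT.TB test". Neither treatment nor a visit is mentioned.
- **Footnote to the table.** For deviations with both sources, "the deviation will show if either source identifies". The footnote also defers detailed programming to the ADaM specification, which is not among the documents.
- **Row [D17].** Under violation of discontinuation criteria: "Patient has a positive TB test using PPD or QuantiFERON®-TB Gold". The action is to keep the subject in the PPS, and the source is the monitor only.
- **A comparable row.** The hepatitis B row, [10], ties its program to screening: "if test positive for HBV at Visit 1 by testing".

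SAP Sections 6.1.1, 6.6 and 6.11.3 make the PPS a Period 2 population, used for a supportive repeat of the co-primary analysis. Section 6.16 also plans a Period 2 summary of important deviations by treatment group and a by-patient listing.

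**The concern.** Whether a deviation removes a subject from the PPS should follow from its definition. Here the definition turns on treatment status for latent TB, while the rule that will be programmed turns on the test result alone. These tests can be positive in a subject whose latent infection has been treated, and for that subject the two columns of the same row disagree.

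At stake are the composition of the PPS, which is the only alternative population that the SAP names for the co-primary endpoints, and the accuracy of the eligibility deviations reported by treatment group. The missing visit limit adds a second uncertainty: whether a test that turns positive after entry counts under row [9], which excludes, or only under row [D17], which does not.

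**Working it through.** This is a comparison of text. No figure in the plan underlies it.

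**Step 1: definition against program within row [9].**

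| Subject | Meets the definition? | Flagged by the program? |
|---|---|---|
| Untreated latent TB, positive test at screening | Yes | Yes |
| Treated latent TB, positive test at screening | No | Yes |
| Active TB, positive test at screening | Yes if untreated; if treated, depends on how the phrase is parsed | Yes |
| Negative at entry, positive on study | Not evidence at entry | Yes, if the missing visit limit is taken literally |

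The second line is the firm mismatch. It holds under either parsing of the definition (the word *untreated* governing both forms of TB, or latent TB only), and it holds whether or not the program is limited to screening.

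**Step 2: can the monitor's list correct it?** No. The footnote joins the two sources by *or*, so a monitor who judges the subject treated and eligible cannot cancel a programmed flag.

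**Step 3: time anchor.** The eligibility rows with a programmed source are [1], [2], [5], [9], [10], [11], [29] and [32].

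- [1] is tied to Visit 2.
- [2] is tied to Visits 1 and 2.
- [5], [10], [11] and [29] are tied to Visit 1.
- [32] is tied to the prior-therapy form.
- [9] alone has no anchor.

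Taken literally, a skin test or QuantiFERON result that turns positive after entry meets both [9] (exclude) and the test result described in [D17] (do not exclude). A positive in Period 3 or 4 would even remove the subject from a Period 2 population. T-SPOT appears in [9] but not in [D17].

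**Step 4: does it matter for power?** The nearest figure in the plan is the power above 99% in SAP Section 5.2.1, for 110 against 55 subjects at response rates of 80% and 10%, by 2-sided Fisher's exact test at 0.05. Exact power is the sum over x and y of Bin(x; n1, 0.80) × Bin(y; n2, 0.10), taken over outcomes with Fisher p ≤ 0.05. For 110 and 55 this exceeds 99.99%, which agrees with the stated figure. The PPS losses below are assumptions; the documents give no TB-positive rate.

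| Assumed loss | Subjects lost | n1 / n2 | Power |
|---|---|---|---|
| 2% | 3 | 108 / 54 | >99.99% |
| 5% | 9 | 104 / 52 | >99.99% |
| 10% | 16 | 99 / 50 | >99.99% |
| 20% | 33 | 88 / 44 | >99.99% |

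The consequence is therefore who is in the PPS and what is reported as a deviation, not loss of power.

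**The case against.** The strongest reply is that row [9] sits under eligibility, so it can concern only status at entry. A conversion on study does not breach an entry criterion, and the unseen ADaM specification may already limit the flag to screening. On that view the missing visit is a drafting omission, and [D17] describes a different deviation at a different stage. A reader might infer that the SAP sets a rule to flag positives at any time and flatly contradicts [D17]. The documents do not support that: the SAP never says so, and the conflict appears only if the missing limit is programmed literally. This part of the reply stands.

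A second reply is that the main protocol's TB criterion is not among the documents, so it cannot be shown that treated latent TB was admissible. That also stands. The baseline summary of TB exposure as positive or negative (SAP Section 6.8.1) shows that positives were foreseen, not that treated ones could enroll. The point therefore rests on row [9]'s own definition.

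Neither reply removes the mismatch in Step 1. Reading the row as screening-only leaves a treated latent-TB subject flagged and excluded. A note deferring programming detail does not replace a condition that the guidance omits.

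The spelling of the skin-test term in the guidance is at most clerical and has no analytic effect.

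**Conclusion.** Row [9]'s guidance does not implement its definition for treated latent TB, and the footnote makes the programmed flag decisive. The missing screening anchor is a secondary gap that creates a clash with [D17] only under a literal reading.

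The number of subjects affected is unknown and may be zero. One could assume a positive-test rate, multiply it by the 165 planned subjects and call the result the number wrongly removed. The documents do not support that: they give no rate, and such a count would include untreated positives at screening, whom the row rightly excludes.

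The effect is confined to the supportive PPS analysis, the Period 2 deviation summary and the deviation listing. The primary analysis (ITT, Fisher's exact test, nonresponder imputation) is untouched. This is a minor point, worth fixing because the correction is cheap.

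**What to change.** Amend the programming guidance for row [9] in four respects:

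1. Use only TB results from screening and baseline (Visit 1 and Visit 2).
2. Do not raise the programmed flag on a positive test where treated latent TB is documented.
3. Keep active TB under the row, as its definition and the main protocol criterion require. A blanket filter on any record of TB treatment could drop treated active cases that the row may be meant to cover, so check the parsing against the main protocol.
4. Leave positives after entry to [D17], and state whether T-SPOT results belong there.

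Correct the skin-test term to induration at the same time. None of this sets a clinical rule; it aligns the program with the SAP's own text.

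The programming cost is small, but the timing needs care. The SAP's revision history places Version 3 after the primary database lock, and Section 6.17 couples that Week 12 lock with unblinding. The table governs a Period 2 population that is already locked. Record the change as a post-lock clarification with its reason, list any subject whose PPS status changes and, if there is one, show the PPS result under both rules. If the ADaM specification already works this way, a note saying so is enough.
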